Interestingly, HNSCCs have been found to express somatostatin receptors (SSTRs). SSTRs have also been found in laryngeal cancer specimens and cancers of the oral cavity and oropharynx, but not in control tissue^{1,2}. Recent studies have found that HPV causes mutations in the same pathways that activate SSTR expression on tumor cells³. These studies suggest a correlation with HPV-positive HNSCC and SSTR expression. This latter group of patients often have non-detectable primary tumors that arise from the oropharynx, an area that normally exhibits ¹⁸F FDG PET/CT uptake thus making tumor localization difficult. Schartinger et al studied SSTR PET/CT in a small series of HNSCC patients and found that all patients showed radionucleotide uptake on imaging⁴. Multiple case reports have been published showing similar uptake for head and neck squamous cell carcinomas by ⁶⁸Ga^{5,6}. An unpublished trial was performed comparing SSTR PET/CT with ¹⁸F FDG PET/CT for 35 patients with HNSCC; the study concluded that SSTR PET/CT had the potential to be more specific for HNSCC than ¹⁸F FDG PET/CT⁷. Unfortunately the study was small, HPV status was not correlated, and recurrent/post-treatment patients were not studied. These studies show that SSTR-specific imaging, such as NETSPOT, has the potential to be equal to and possibly more specific than ¹⁸F FDG PET/CT for HNSCC patients, especially in the setting of HPV positivity, unknown primary site tumors, and post-treatment follow-up. More importantly, a therapeutic target for SSTRs is widely available; as such, HNSCC patients who show clinical uptake on NETSPOT imaging may be candidates for future studies using targeted therapeutics.

Objectives and study aims:

List the primary/secondary objectives to correspond directly with the listed hypotheses; define the role of AAA compounds

Study Aim:

Evaluate utility of NETSPOT imaging for disease detection in HNSCC, as well as the potential for targeted receptor-specific therapeutics.

Primary Objectives:

To determine the utility of NETSPOT imaging, as compared to ¹⁸F FDG PET/CT, in detection and staging of HNSCC.

To evaluate the potential of NETSPOT imaging in guiding the use of targeted radiopeptides for HNSCC treatment.

Secondary Objectives:

To determine if NETSPOT imaging and ¹⁸F FDG PET/CT, when used together, can lead to improved tumor delineation and detection of metastatic disease.

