To determine the imaging characteristics of NETSPOT versus ¹⁸F FDG PET/CT in the setting of inflammation.

To determine if NETSPOT imaging uptake correlates with tumor HPV-positivity.

To determine if patients with tumor uptake on NETSPOT imaging exhibit different disease outcomes than patients without uptake.

Hypothesis:

List the clinical hypotheses in order of priority

NETSPOT imaging will be at least equivalent to ¹⁸F FDG PET/CT in the detection and staging of HNSCC.

The combination of NETSPOT imaging and ¹⁸F FDG PET/CT, will have increased specificity for detecting the primary site for HNSCC of unknown primary than ¹⁸F FDG PET/CT alone.

The combination of NETSPOT imaging and ¹⁸F FDG PET/CT, will have increased specificity for detecting disease recurrence and metastasis following treatment than ¹⁸F FDG PET/CT alone.

Is a study protocol already available (Yes/No)? If yes, please attach to the IIS form

No.

Study Design/Clinical Plan:

Provide a concise overview stating the type of experimental design (for ex, randomized/non-randomized, condensed eligibility criteria etc)

Design: This study will be designed as a “proof-of-concept” trial to compare NETSPOT with ¹⁸F FDG PET/CT for HNSCC.

Inclusion Criteria:

HNSCC patients undergoing planned ¹⁸F FDG PET/CT at time of primary diagnosis.

HNSCC patients undergoing planned ¹⁸F FDG PET/CT for unknown primary site.

HNSCC patients undergoing planned ¹⁸F FDG PET/CT after completion of adjuvant treatment.

Exclusion Criteria:

Inability to undergo ¹⁸F FDG PET/CT imaging due to medical comorbidities.

Enrollment:

Patients meeting inclusion criteria will be enrolled on evaluation. Based on our current clinical volume, we plan to enroll 30 patients over a 6 month time frame.

Preliminary analysis (outlined below) will be done after the first 30 patients to assess the utility of NETSPOT imaging in HNSCC.

Treatment:

List the clinical dosage/dosage form, route, and dose regimen

Brief Overview:

Patients meeting inclusion criteria will be consented at the time of scheduling.

All patients will undergo ¹⁸F FDG PET/CT per established protocol.

Following ¹⁸F FDG PET/CT, the patient will undergo NETSPOT imaging with the AAA-provided dose. These scans will be performed no less than 24 hours, no more than 7 days apart.

Analysis:

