Both ¹⁸F FDG PET/CT and NETSPOT images will be reviewed by the senior radiologist and the primary surgeon for concordance between images. SUV will be measured for both images and recorded.

Patients will undergo clinical follow-up based on ¹⁸F FDG PET/CT results as per protocol.

True positive results will be recorded for both ¹⁸F FDG PET/CT and NETSPOT images and analyzed for sensitivity and specificity.

For patients undergoing surgical treatment, pathology results including routinely reported HPV markers will be recorded and compared to NETSPOT imaging characteristics.

Follow-up

All enrolled patients will be followed for 1 year after imaging.

Expected Results/Outcomes:

We expect that ¹⁸F FDG PET/CT and NETSPOT will have similar uptake and specificity for primary tumor. We hypothesize that NETSPOT will have increased specificity for unknown primary site tumor and recurrent or metastatic disease. Finally, we hope that NETSPOT positivity in HNSCC will allow for future study of targeted radionuclide therapies for HNSCC.

Applicability of Results:

Any other information regarding the medical need and/or the strategic importance of the research which may help the committee's evaluation

A proof-of-concept trial to compare SSTR/ PET/CT with ¹⁸F FDG PET/CT in the head and neck cancer population would be a novel use of the NETSPOT technology. The study is warranted based on past data and the potential for success, especially in patients with oropharyngeal tumors, previous radiation or inflammatory disease; all of whom ¹⁸F FDG PET/CT is difficult to interpret. If the hypothesis is supported, Advanced Accelerator will have a new application for the NETSPOT technology and a new area for business development and revenue.

Additional Research (if applicable):

Histology, biomarkers, PK etc.

Statistical Plan:

Include justification for clinical sample size and primary hypothesis testing

Statistical Considerations:

The primary objective of this study is to evaluate SSTR receptor expression in the head and neck cancer population. The secondary objective is to assess the concordance based on SSTR PET/CT with and without FDG PET/CT outcomes.

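### The statistical section's primary objective does not match the stated objectives and first hypothesis, and the sized paired non-inferiority test is missing from the analysis methods

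*Combined protocol and SAP*

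**What the plan says.** **Objectives.** The Primary Objectives list two items without ranking them. One begins "To determine the utility of NETSPOT imaging, as compared to" FDG PET/CT, for detection and staging. The other is "To evaluate the potential of NETSPOT imaging in guiding the use of targeted radiopeptides for HNSCC treatment".

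**Hypotheses.** These are ranked, because the form's prompt reads "List the clinical hypotheses in order of priority". The first begins "NETSPOT imaging will be at least equivalent to" FDG PET/CT.

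**Statistical Considerations.** This section opens with "The primary objective of this study is to evaluate SSTR receptor expression in the head and neck cancer population". Its secondary objective is a concordance assessment of SSTR PET/CT with and without FDG PET/CT.

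**Methods listed there.** They are a t-test and Fisher's exact test on SSTR expression, then sensitivity and specificity of the new method with binomial 95% intervals. The clinical Analysis section adds that true positives are recorded for FDG PET/CT and "NETSPOT images and analyzed for sensitivity and specificity", but names no paired comparison.

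**Sample Size.** A one-sided non-inferiority test for two correlated proportions is described here and nowhere else: concordance 0.90, margin 0.15, alpha 0.10, 30 subjects, 81% power. The t-test (0.95 SD, 15 per group, two-sided 0.10) also has a stated power of 81%.

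**The concern.** An analyst who works from the Statistical Considerations would report SSTR-expression tests, single-method accuracy with 95% intervals, and a concordance figure. None of these says whether NETSPOT is within 15 points of FDG PET/CT, which is the question posed by the first-ranked hypothesis and the one for which the plan claims 81% power.

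If the sample-size paragraph is read as the analysis plan, two choices remain open. One is which proportion is compared: the paragraph cites FDG sensitivity, specificity and accuracy across primary, nodal and recurrent disease. The other is which form of the paired test is used. Both could be settled after the results are known.

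**Working it through.** **Inputs, all from Sample Size:** n = 30, margin m = 0.15, concordance 0.90 (so discordance 0.10), one-sided alpha 0.10 (critical z 1.2816). A true difference of 0 is my assumption; the plan does not state one. Let b be the number of patients positive on NETSPOT only and c the number positive on FDG PET/CT only.

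**Step 1: reproduce the plan's figures.**
- t-test: noncentrality 0.95/√(2/15) = 2.60 on 28 df, two-sided 0.10, gives power 0.814. The stated 81% holds.
- Paired score test, asymptotic: the per-patient null variance is v₀ = 2q + m − m², with q the restricted estimate. Here q = 0.0254 and v₀ = 0.178. Power = Φ[(0.15√30 − 1.2816√0.178)/√0.10] = Φ(0.887) = 0.812. Exact enumeration over all (b, c) gives 0.811. The stated 81% holds.
- Paired Wald test: Φ(0.15√(30/0.10) − 1.2816) = Φ(1.317) = 0.906 asymptotically and 0.873 exactly. Neither matches 81%.

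The plan's figure is therefore consistent with a score test in which all 30 patients count.

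**Step 2: can a concordance rate stand in for the test?**

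Score z = [nm − (c − b)]/√[n(2q + m − m²)], where q is the larger root of 2nq² + [−(b + c) + (2n − (c − b))m]q − bm(1 − m) = 0. Here nm = 4.5.

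| b vs c | concordant | q | score z | lower 80% limit | non-inferior? |
|---|---|---|---|---|---|
| 1 vs 2 | 27/30 | 0.0183 | 3.5/√4.926 = 1.58 | −12.3 points | shown |
| 0 vs 3 | 27/30 | 0 | 1.5/√3.825 = 0.77 | −19.2 points | not shown |

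Both rows have exactly the planned concordance of 0.90, yet the conclusions are opposite.

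**Step 3: can the single-method intervals stand in?** An interval for NETSPOT alone contains no comparator. Intervals for both scans fix the difference in proportions but not the number of discordant patients, which determines the paired variance. For example, take NETSPOT 25/30 (exact 95% interval 65.3% to 94.4%) and FDG 26/30 (69.3% to 96.2%). These totals fit 1 vs 2 (z 1.58, shown) and also 4 vs 5 (z 1.14, limit −16.5, not shown). The second split is an illustration of principle only: at the planned concordance, nine or more discordant patients has probability about 0.2%.

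The levels also differ. One-sided 0.10 corresponds to a two-sided 80% interval for the paired difference, not a 95% interval.

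**Step 4: does the test form matter?** For 0 vs 2, score z = 2.5/√3.825 = 1.278, just below 1.2816 (not shown). Wald z = 2.5/√(2 − 4/30) = 1.83 (shown). Summed over all outcomes under the plan's assumptions, the two forms disagree about 6% of the time.

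**Step 5: does the choice of proportion matter?** If it is sensitivity, only diseased patients count. Eligible patients include those having "FDG PET/CT after completion of adjuvant treatment", some of whom may be disease-free. The documents give no expected count. For assumed counts of 25, 20 and 15, score power is 75%, 66% and 55% asymptotically, and 82%, 65% and 66% exactly. The exact values are not monotone because the outcome is discrete.

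**The case against.** The strongest reply is that the test is already planned. The Statistical Plan is one short section, and its prompt reads "Include justification for clinical sample size and primary hypothesis testing". The answer names a test, margin, alpha and power, so the sample-size paragraph can be read as stating the primary test. This largely stands. A reader might infer that the first hypothesis has no test at all, and the documents do not support that. What remains is that the listed methods omit the test, and the paragraph does not say which proportion is compared or which form is used.

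Second, the conflict over objectives is narrower than it first looks. The two primary objectives are not ranked against each other, and SSTR expression plausibly serves the one on radiopeptides. The secondary concordance wording is ambiguous: it may concern using both scans together rather than demoting the head-to-head comparison. On either reading, that comparison is absent from the statistical section's primary objective.

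Third, the unit and the patients are not really open. The test is sized on 30 subjects and every patient is to have both scans, which points to a per-patient comparison of all 30. That stands.

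Fourth, the 0 vs 2 case is a knife-edge and the 4 vs 5 case is very unlikely. Both are fair criticisms, and the frequencies are given above. The 27/30 comparison needs neither case.

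Fifth, this is a preliminary proof-of-concept study. That lowers the consequence, but the plan itself chose a formal margin, alpha and power.

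**Conclusion.** The point holds as an internal inconsistency that should be fixed. The statistical section's primary objective does not match the Primary Objectives or the first-ranked hypothesis, and its listed methods omit the test that sizes the comparison. Followed literally, those methods cannot give the non-inferiority conclusion; at the planned 27/30 concordance, the conclusion turns on how three discordant patients split.

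Two further inferences are tempting but unsupported. One is that the stated power is wrong: both 81% figures reproduce, and none is lost with a score test, all 30 patients and a true difference of 0. The other is that the proportion and form will be picked to suit the data: the documents do not say when they are settled, so only the possibility can be claimed. The effect of test form is limited to about 6% of outcomes under the plan's assumptions. Any power loss from counting only diseased patients rests on assumed counts.

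**What to change.** - Align the statistical section's objectives with the Primary Objectives and Hypothesis sections. Make the FDG PET/CT comparison a primary objective, and keep SSTR expression, with its own power calculation, under the radiopeptide objective.
- Move the sized paired non-inferiority test (margin 0.15, one-sided 0.10) into the analysis methods as the primary analysis of the first hypothesis.
- Name the per-patient proportion compared and the test form. A score test matches the stated 81%.
- Report the paired difference with a two-sided 80% interval, and keep single-method 95% intervals for both scans as descriptive.
- If the proportion is sensitivity, restate power for the expected number of diseased patients.

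The cost is wording and one standard analysis of data already collected. N, margin and alpha stay as they are. The stated power may fall if not all 30 patients count.

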A Student t-test will be used to assess the difference of SSTR expression between the diagnostic results (positive vs negative) and Fisher's exact test will be used to assess the association between dichotomized expression (high vs low) and a binary outcome (positive vs negative). The sensitivity will be estimated by a proportion of true positives that are correctly identified by the new method. The specificity will be estimated by a proportion of true negative that are correctly identified by the new method. The corresponding 95% confidence intervals will be estimated based on binomial distributions.

Sample Size: Based on the two-sided t-test, a sample size of 30 will have 81% power to detect 0.95 standard deviations of the SSTR expression between positive and negative outcomes (15 per group) at a 0.10 significance level. In addition, based on the historical data and current literatures, head and neck squamous cell carcinoma (HNSCC) makes up 90% of head and neck cancers. For primary tumor detection, 18F FDG PET/CT is about 96% sensitive (oral cavity only) and anywhere from 91%-98% accurate at detecting lymph node metastasis, with sensitivity of 67%-79%, and specificity of 82-95%. For detecting recurrent disease, 18F FDG PET/CT is ranged from 83%-100% sensitive and 90-98% specific. Based on one-sided non-inferiority test for two correlated proportions with a concordance of 0.90, when the maximum allowable difference between these proportions that still results in non-inferiority (the range of non-inferiority) is 0.15, a sample size of 30 subjects achieves 81% power at a significance level of 0.10.

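### No stated analysis compares NETSPOT plus FDG with FDG PET/CT alone, the contrast in hypotheses 2 and 3

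*Combined protocol and SAP*

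**What the plan says.** Under Hypothesis, the second item says that the combination "will have increased specificity for detecting the primary site for HNSCC of unknown primary than ¹⁸F FDG PET/CT alone". The third says that it "will have increased specificity for detecting disease recurrence and metastasis following treatment than ¹⁸F FDG PET/CT alone". Both name the same comparator and the same measure.

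The related item under Secondary Objectives asks whether the two scans, "when used together, can lead to improved tumor delineation and detection of metastatic disease", but names no comparator.

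Under Statistical Considerations the combination appears once: "The secondary objective is to assess the concordance based on SSTR PET/CT with and without FDG PET/CT outcomes". The methods that follow are a t-test and Fisher's exact test on SSTR expression, and estimates of sensitivity and specificity for one modality: "The specificity will be estimated by a proportion of true negative that are correctly identified by the new method". The sample-size paragraph adds a paired non-inferiority calculation that does not mention the combination.

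The Analysis section under Treatment says that results for both FDG and NETSPOT are recorded, the "images and analyzed for sensitivity and specificity". It also has the radiologist and the surgeon review both scans for concordance. No section says how a combined NETSPOT plus FDG result is formed.

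**The concern.** FDG PET/CT is described in the background as the current standard, with specificity limited by inflammation, infection or earlier radiation. The clinical question behind hypotheses 2 and 3 is therefore what NETSPOT adds to FDG. An analysis that answers it needs FDG alone on one side and FDG plus NETSPOT on the other, scored in the same patients. The Statistical Plan's sentence has SSTR PET/CT on both sides and treats FDG as the part added or removed, which asks what FDG adds to NETSPOT. If that sentence is followed, two of the three listed hypotheses end the study without a matching result.

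**Working it through.** **1. The plan's own figures.** Two power statements are given, each 81% with 30 patients.

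- t-test: 15 per group, 0.95 SD, two-sided alpha 0.10. Noncentrality = 0.95 × √(15/2) = 2.60 on 28 degrees of freedom; power 81.4%.
- Paired non-inferiority: concordance 0.90 (discordance 0.10, taken as split equally), margin 0.15, one-sided alpha 0.10. The score test gives 81.2% asymptotically and 81.1% by exact enumeration.

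Both reproduce. Neither concerns the combination, so neither is affected by this point.

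**2. Which analyses supply the contrast.**

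| Text | NETSPOT + FDG present? | FDG alone present? |
|---|---|---|
| Hypotheses 2 and 3 | yes | yes |
| Secondary objective in the Statistical Plan, literal | yes | no |
| Same sentence, read as SSTR–FDG agreement | no | yes |
| Sensitivity and specificity in the Statistical Plan | no (new method only) | no |
| Sensitivity and specificity in the Analysis section | no (each scan separately) | yes |

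No row below the first has both.

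**3. What the literal contrast measures.** Among m patients without disease, let a = FDG+/NETSPOT+, b = FDG+/NETSPOT−, c = FDG−/NETSPOT+, d = FDG−/NETSPOT−. Then specificity is (c + d)/m for FDG and (b + d)/m for NETSPOT.

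- Both-positive rule: combined specificity is (b + c + d)/m. The gain over FDG is b/m; the gain over NETSPOT is c/m.
- Either-positive rule: combined specificity is d/m. The change from FDG is −c/m, so specificity can never rise.

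Of these two simple rules only both-positive can produce the gain that the hypotheses predict. Under it, the b patients are FDG false positives corrected by NETSPOT. For them the combined result and the NETSPOT result are both negative, so the literal measure scores them concordant. It counts the c patients instead.

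**4. Illustration in specificity.** FDG specificity 0.90 is the low end of the plan's 90–98% for recurrence. Concordance 0.90 is borrowed from the non-inferiority calculation and assumed to hold among non-diseased patients. NETSPOT specificity is not given, so a range is assumed. With false-positive rates f and g, the proportion positive on both scans is (f + g − 0.10)/2, and combined specificity is 1 minus that.

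| NETSPOT specificity (assumed) | Positive on both | Combined | Gain over FDG | Gain over NETSPOT (literal) |
|---|---|---|---|---|
| 0.85 | (0.10 + 0.15 − 0.10)/2 = 0.075 | 0.925 | 0.025 | 0.075 |
| 0.90 | (0.10 + 0.10 − 0.10)/2 = 0.050 | 0.950 | 0.050 | 0.050 |
| 0.95 | (0.10 + 0.05 − 0.10)/2 = 0.025 | 0.975 | 0.075 | 0.025 |

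The two gains agree only where the scans have equal specificity.

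**5. Illustration in patients.** With 30 patients and 0.90 concordance, 30 × 0.10 = 3 are discordant. Under both-positive, if all 3 are FDG+/NETSPOT−, the literal measure gives 30/30 = 100%, while combination and FDG agree in 27/30 = 90%. If all 3 are FDG−/NETSPOT+, the two figures swap. These are the extreme splits, and they pool diseased and non-diseased patients.

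**The case against.** The sentence is loosely worded, and a fair reader could take it as plain agreement between SSTR and FDG results. The Analysis section uses concordance in that sense, and the 0.90 in the sample-size paragraph belongs to a paired comparison of two proportions, which fits the first hypothesis (NETSPOT against FDG). On that reading FDG alone is present. This stands as a reading, but it has no combination in it, so hypotheses 2 and 3 remain unanswered.

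FDG-alone sensitivity and specificity are also planned in the Analysis section. That stands too: FDG alone is missing from the literal combination measure, not from the study.

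A reader might go further and infer that the plan will judge hypotheses 2 and 3 on the wrong contrast and reach a wrong answer. The documents do not support that. Both hypotheses are about specificity, and nothing says that they will be decided on concordance. Nor does the cell argument hold for every possible combination: a joint call by the radiologist and surgeon need not follow either simple rule. The defect is a missing analysis with a sentence that points the other way.

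Finally, this is a 30-patient proof-of-concept study. That excuses wide intervals, but not leaving the comparison unspecified.

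**Conclusion.** The point holds as an omission: on no reading does the plan, as written, compare NETSPOT plus FDG with FDG alone. On the literal reading with a both-positive rule, the written measure also misses the patients whom hypotheses 2 and 3 concern.

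The size cannot be derived. The documents give no combination rule, no NETSPOT specificity, no expected gain and no number of non-diseased patients in the unknown-primary or post-treatment groups. The figures of 0.025 to 0.075 and the 3-of-30 splits rest on assumed inputs and show direction only. No power can be computed for the missing comparison.

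**What to change.** 1. Reword the secondary objective in the Statistical Plan as FDG PET/CT with and without SSTR PET/CT. NETSPOT with and without FDG can stay as a descriptive extra.
2. State in advance how the combined result is formed: for example both scans positive, or a recorded joint call by the radiologist and surgeon who already review both. Rewording alone does not make the hypotheses testable.
3. Among patients without disease on final status, separately in the unknown-primary and post-treatment groups, tabulate FDG alone against FDG plus NETSPOT. Report the paired difference in specificity (patients corrected, patients made wrong) with a paired interval. Every patient in the unknown-primary group has HNSCC by inclusion, so say there what counts as a negative: a patient with no confirmed primary, or a tumour-free site.
4. Report the paired change in sensitivity in diseased patients alongside, because a both-positive rule can only lower sensitivity relative to FDG.

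Cost: a reworded sentence, a stated rule and small paired tables from scans already planned in the same 30 patients. A joint call would add one recorded item per patient. The comparison will rest on few discordant patients, so its intervals will be wide and it should be presented as estimation.
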